7.2.1 Statistical Analysis Plan

All analyses will be conducted under intention-to-treat principles.

7.2.2 Aim 1. Feasibility/Acceptability

We will measure response rates for follow-up data collection using the online survey functionality in REDCap. We will use descriptive statistics to characterize response rates by study arm and demographic characteristics. We will use generalized estimating equations (GEE) with a working correlation matrix to estimate a logistic regression model for response vs. non-response. We will estimate separate models for the 8-week and 24-week outcome periods. Models will be adjusted for PLWD stage of dementia (DSRS), PLWD FAQ score, PLWD age and sex, caregiver relationship (spouse, non-spouse), caregiver age and sex, caregiver highest level of education attained, PLWD residential status (living with caregiver full-time versus not) and study arm.

7.2.3 Feasibility/Acceptability - Completion of Training.

We will use descriptive statistics to characterize completion rates by study arm and demographic characteristics. We will use generalized estimating equations (GEE) with a working correlation matrix to estimate a logistic regression model for completion vs. non-completion. Models will be adjusted for PLWD stage of dementia (DSRS), PLWD FAQ score, PLWD age and sex, caregiver relationship (spouse, non-spouse), caregiver age and sex, and caregiver highest level of education attained, and study arm.

7.2.4 Assess the feasibility and acceptability from the payer perspective.

We will use descriptive statistics to characterize the effort required by coaches to facilitate caregiver training. These measures are (1) time reading secure messages, (2) number of exchanges per message thread, (3) number of ad hoc phone calls required (i.e., other than the 6 scheduled calls).

7.2.5 Primary Care, Urgent Care and Emergency Department Use.

We will use longitudinal, generalized estimating equations (GEE) to estimate a Poisson regression model for adjusted mean monthly visit rates (separately by visit type) in the STAR-VTF arm compared to the attention control arm in the 6 months following randomization. Models will be adjusted for PLWD stage of dementia (DSRS), PLWD FAQ score, PLWD age and sex, caregiver relationship (spouse, non-spouse), caregiver age and sex, and caregiver highest level of education attained, and study arm. We will use the robust sandwich estimator to calculate standard errors to account for repeated (i.e. 6 monthly) observations within people and the misspecified variance in the Poisson model.

7.2.6 Effect of STAR-VTF on CG burden and PLWD antipsychotic medication use.

We will measure overall caregiver burden using the Revised Memory and Problem Behavior Checklist (RMPBC). We will use GEE with a working correlation matrix to estimate the regression model, using robust sandwich estimators to calculate standard errors accounting for within person correlation. We will adjust for baseline pre-randomization covariates: PLWD stage of dementia (DSRS), PLWD FAQ score, PLWD age and sex, caregiver relationship (spouse, non-spouse), caregiver age and sex, and caregiver highest level of education attained.

We will use generalized estimating equations (GEE) with a working correlation matrix to estimate a logistic regression model for refill (versus no refill) of the initial antipsychotic medication. Models will be adjusted for PLWD stage of dementia (DSRS), PLWD FAQ score, PLWD age and sex, caregiver relationship (spouse, non-spouse), caregiver age and sex, and caregiver highest level of education attained, study arm. We will again use GEE with a working correlation matrix to estimate a logistic regression model for daily versus “less than daily” use of antipsychotic medication (as reported to the coach). Models will again be adjusted for pre-randomization variables listed above.

7.2.7 Caregiver depression, stress and self-efficacy.

Caregiver depression will be measured using the PHQ-8. Caregiver self-efficacy will be measured using the Caregiver Mastery Scale. Caregiver stress will be measured using the Kingston Caregiver Stress Scale. We will again use GEE to compare the mean PHQ-8, CMS and Kingston scores in the STAR-VTF and attention control arms. Models will be adjusted for pre-randomization variables as above.

7.3 *Handling of Missing Data*

Preventing missing data is superior to statistical treatment. We will make every effort to collect data on all study participants. If there are substantial missing data or significant loss-to-follow-up, we will use inverse probability weighting(23) to rebalance the STAR-VTF and attention control group. Inverse probability weights are used to rebalance groups on prognostic factors when the treatment and control groups become unbalanced over time, post-randomization, due to study drop out. If we find intermittent missing data, we will instead use multiple imputation(24) via chained equations to address the problem, using at least 10 imputed datasets and combining results using Rubin's rules.

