7 STATISTICAL CONSIDERATIONS

7.1 *Sample Size Considerations*

We anticipate enrolling 100 PLWD-CG dyads in the trial (50 per arm), with up to 90 remaining enrolled at 6 months of follow-up (i.e., 10% lost to follow-up).

7.1.1 Statistical Power for Primary Outcome.

We calculated effect sizes for the impact of STAR-C on the Subjective Caregiver Burden scale ($d=0.77$) and the Revised Memory and Behavior Problem Checklist ($d=0.68$) based on the p-values reported for t-tests comparing the STAR-C mean with the routine medical care group mean in prior research. We will power on the RMBPC (primary outcome) and assume a loss of effect size due to the lower intensity of the intervention. Assuming an effect size of 0.65, type-I error of 0.05, power of 80%, and equal sample sizes, we will require 39 dyads in the STAR-VTF arm and 39 dyads in the control arm ($n=78$). We additionally assume it will be necessary to adjust for baseline covariate imbalance and sample attrition, thus, we will inflate our recruitment targets by 30% as we have done in the past. The final recruitment target will be 50 PLWD-CG dyads in each arm.

7.2 *Analysis Plan*

Data will be collected from project tracking systems, the Epic EMR, and other health system data systems for analysis. Baseline, 8 week, and 6 month measures will be collected via an online survey using REDCap functionality.

Data validation and quality assurance checks will be undertaken to ensure data collection during the study is sufficiently reliable.

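### The planned response/non-response logistic model has 10 to 12 slopes for about 10 expected non-responders, so it may have no finite estimate and overstates non-null effects when it fits

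*Protocol*

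**What the plan says.** Section 7.2.2 of the protocol first plans descriptive response rates by arm and by demographic group. It then plans, by GEE, to "estimate a logistic regression model for response vs. non-response". Visits are not pooled: "We will estimate separate models for the 8-week and 24-week outcome periods". The adjustment set is long: "Models will be adjusted for PLWD stage of dementia (DSRS), PLWD FAQ score, PLWD age and sex, caregiver relationship (spouse, non-spouse), caregiver age and sex", followed by "caregiver highest level of education attained, PLWD residential status (living with caregiver full-time versus not) and study arm".

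The numbers come from section 7.1. It sets the target at 100 dyads, 50 in each arm. On retention it expects the trial to run "with up to 90 remaining enrolled at 6 months of follow-up (i.e., 10% lost to follow-up"). No survey non-response rate is given for either time point.

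Response rates at baseline, 8 weeks and 6 months are secondary outcome 5 in section 3.2, defined as the proportion completing the measures. Neither document gives a coding for education, a penalised or exact method, a rule for non-convergence, or a rule for shortening the covariate list. The SAP contains no response model, so section 7.2.2 is the only specification.

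**The concern.** A logistic model is limited by the rarer outcome, here non-response. With about as many slopes as non-responders, two things go wrong. Some combination of covariates may separate responders from non-responders perfectly, completely or in part, and then at least one coefficient has no finite maximum-likelihood estimate. When the estimates are finite, small-sample bias pushes non-null log odds ratios away from zero.

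At stake is a prespecified secondary analysis that may have to be repaired after the data are seen, by dropping covariates or merging education levels. Avoiding such choices is the purpose of a plan. If nothing fails visibly, the reported predictors of non-response will look stronger than they are.

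**Working it through.** **The plan's own figures.** With a standardised effect of 0.65, two-sided alpha 0.05 (sidedness assumed) and 80% power, the t-test needs 38.14, so 39 per arm, as stated. Inflating by 30% gives 39 × 1.30 = 50.7, against 50 stated. Expected losses are 100 × 0.10 = 10, which matches 100 − 90 = 10.

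**Slopes.** Dementia stage, functional score, age and sex of the person with dementia, relationship, and caregiver age and sex make 7. Residential status and arm add 2. Education adds 1 if linear and k − 1 if it has k levels. The total is 10 (linear), 11 (three levels) or 12 (four levels), plus an intercept.

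**Events per slope with 10 non-responders.** 10/10 = 1.00; 10/11 = 0.91; 10/12 = 0.83.

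**Why GEE does not help.** With one binary record per dyad in each model, the working correlation matrix is 1 × 1. The estimating equation Σ xᵢ(yᵢ − pᵢ) = 0 is then the ordinary logistic score equation. Robust standard errors change the variance but not the existence or bias of the estimate.

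**Separation by simulation.** Trials of 100 dyads were generated with assumed covariate distributions (independent, or with dyad-like correlations), at 500 to 3,000 trials per setting. Separation exists if some non-zero b satisfies (2yᵢ − 1)xᵢ′b ≥ 0 for every dyad, strictly for at least one. This was tested by linear programming. The ranges below run across all settings.

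| Education coding | Slopes | No finite estimate, 10% non-response | 20% non-response |
|---|---|---|---|
| Linear | 10 | 4% to 17% | 0% to 2% |
| Three levels | 11 | 12% to 28% | 0.4% to 1.4% |
| Four levels, none sparse | 12 | 28% to 41% | 5% to 8% |
| Four levels, one sparse (about 10% of dyads) | 12 | 48% to 58% | 11% to 17% |
| Arm only | 1 | 0% to 2.4% | – |

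The linear and three-level figures at 20% are from the runs with 500 trials per setting. With 5% non-response and three levels, the figure is 64% to 69%.

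**Hand check.** A level holding 10 dyads contains no non-responder with probability 0.9^10 = 0.35, and that alone makes the estimate infinite. At 20% non-response it is 0.8^10 = 0.11. With four levels of 25, the chance that at least one is empty of non-responders is about 1 − (1 − 0.9^25)^4 = 1 − (1 − 0.072)^4 = 0.26. For arm alone it is 2 × 0.9^50 = 0.01. These are of the simulated order; the remaining covariates account for the rest.

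**Bias when finite, 10% non-response.** For an assumed true arm odds ratio of 2 (log 0.69), the mean finite estimate was mostly 0.80 to 0.93. The ratios are 0.80/0.693 = 1.15 and 0.93/0.693 = 1.34, an inflation of about 15% to 35%. Some four-level runs gave 1.03 to 1.07 (about 50%), from only 296 and 333 finite fits. With true effects of zero the means were 0.01 and −0.01. With Firth's penalty the mean was 0.61 to 0.71, and no separation failure can arise because the penalised estimate is finite.

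**The case against.** The strongest reply has four parts.

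- **The 10 is not a non-response count.** It is loss to follow-up at 6 months, and the wording makes it a minimum. Enrolled caregivers may also skip the survey, and the sample-size section leaves room for 100 − 78 = 22 losses. With 20 non-responders most of the separation disappears. This stands, and it is why the result is given as a range. It does not settle the matter: response at 8 weeks could be better than at 6 months, and fewer non-responders make the model worse.
- **The rate depends on coding.** With education as a single term the failure rate is about 10%. This also stands, but the protocol does not choose that coding.
- **Separation on education can leave the arm coefficient finite.** This is true, so a failed fit does not always lose the arm comparison.
- **This is a secondary feasibility regression, and descriptive rates by arm are already planned.** This is true, and it limits the consequence.

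A reader might infer more than the documents support:

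- That the model would fail in most trials. This needs a sparse education level, which is only one possible coding.
- That differential response between arms could not be judged. The planned descriptive rates by arm do not depend on the model.
- That half of Aim 1 is lost. Aim 1 in section 2.2 names contact rates and training completion, not survey response.
- That the section 7.2.6 plan to "estimate a logistic regression model for refill (versus no refill) of the initial antipsychotic medication" has the same defect. No refill rate is given, so events per slope are unknown there, and the SAP's adjustment for fills is already short (gender, age and baseline score).

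**Conclusion.** The concern holds for the response model in section 7.2.2. At the protocol's own loss figure the model has about one non-responder per slope or fewer, and no fallback is stated. The chance of no finite estimate is roughly 5% to 55%, governed mainly by the unstated education coding, and about 0% to 17% if 20 dyads do not respond. Inflation of non-null log odds ratios is roughly 15% to 35% when the model fits.

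These figures rest on three assumptions: loss to follow-up stands in for survey non-response, the covariate distributions were chosen for the simulation, and the true arm odds ratio of 2 is illustrative. The slope count and the one-record-per-dyad argument rest on the text alone. The caregiver-burden analysis is untouched. The point is worth correcting because the repair is cheap and the alternative is an unplanned choice after the data are seen.

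**What to change.** In section 7.2.2, for each time point:

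1. Keep the descriptive rates, and add the difference in response proportions between arms with an exact or score 95% interval. Name this as the main between-arm comparison.
2. Fit the logistic model with Firth's penalty. Either enter education as a single term, or limit the covariates to arm and the three randomization factors (caregiver age group, sex, spouse or non-spouse). The second option has 4 slopes, or 10/4 = 2.5 events per slope at 10 non-responders, so the penalty is still needed.
3. State the education coding in advance.

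The cost is a few sentences of text and a standard penalised fit. The downside is fewer, or shrunken, adjusted odds ratios for predictors of non-response, which a feasibility study may want. Keeping the longer list with education as one term and the penalty preserves more of them, at the price of wide intervals.

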Précis:	The STAR-Caregivers program is an education, training, and support intervention demonstrated efficacious in reducing the behavioral and psychological symptoms of dementia. The investigators propose to test a 6-session, self-directed, online version called STAR-virtual training and follow-up (STAR-VTF) that leverages secure email within the member portal at Kaiser Permanente Washington, an online learning management system, and 6 30-minute coaching telephone calls to improve access to training, fidelity to the STAR principles, and to lower the cost of the program. Outcomes in the intervention arm will be compared to an attention control group that receives printed materials and links to online training resources but does not receive coaching.
Objectives:	Test the effectiveness of the intervention training vs. attention control in a practical clinical trial involving one hundred caregiver-person living with dementia dyads at Kaiser Permanente Washington.
Populations:	Persons living with dementia and their informal caregivers (spouses and adult children)
Site:	Kaiser Permanente Washington
Description of Intervention:	This study evaluates the effectiveness of a caregiver outreach, self-directed online training, and support program for caregivers of people with dementia who are using an antipsychotic medication to manage agitation/aggression. The Investigators will conduct a randomized trial of the caregiver program compared to a control group to measure differences in caregiver burden and discontinuation of antipsychotic medication use. The results will help in expanding access to and delivery of empirically supported behavioral health services for caregivers and persons living with dementia.
Trial Duration:	18 months
Subject Participation Duration:	6 months
Estimated Time to Complete Enrollment:	12 months

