The STAR-Caregivers program is an education, training, and support intervention demonstrated efficacious in reducing BPSD.(9, 10, 20, 21) The original program involved 8 face-to-face, in-home training sessions and 4 follow-up phone calls. The condensed version involves 4 in-home sessions with 2 phone follow-ups.(18) Neither of these is feasible from a payer perspective due to the cost and, more recently, the COVID-19 pandemic makes home visits risky. We will test a self-directed, online version called STAR-virtual training and follow-up (STAR-VTF) that leverages weekly telephone calls and secure email within the member portal at Kaiser Permanente Washington to improve access to training, fidelity to the STAR principles, and to lower the cost of the program.

This trial will ascertain the feasibility and acceptability of STAR-VTF in which (a) caregiver training materials are delivered electronically and learning is self-directed, (b) caregivers have 7 telephone calls with a social worker and (c) where caregivers receive ongoing support from a social worker via secure messaging in the web-based portal (My Kaiser Permanente). We will compare outcomes in the STAR-VTF group to an attention control group that receives mailed material from the Alzheimer's Association and National Institute of Mental Health plus generic secure messages. Our specific aims are:

AIM 1: Assess the feasibility and acceptability of conducting caregiver outreach, training, and support via social workers and licensed mental health counselors including: (1) willingness of caregivers to interact through secure messaging (contact rates) and telephone; and (2) willingness of caregivers to complete self-directed training (training completion rates).

AIM2: Assess the feasibility and acceptability of the program from the payer perspective including: (1) average time spent per orientation visit; (2) average time per month spent responding to caregiver emails and coordinating care with primary care physicians; and (3) differences in face-to-face primary care, urgent care, and emergency department visit rates by PLWD.

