3.2 Secondary Outcomes

The following secondary outcome measures for the trial will be assessed:

- (1) **Antipsychotic medication Use.** Proportion of participants will at least one antipsychotic prescription refill after initial medication dispensing, using automated system pharmacy data.
- (2) **Change in caregiver depression.** Self-reported caregiver depression assessed by the 8-item Patient Health Questionnaire (PHQ-8). The PHQ-8 is an eight-item measure of depression that assesses symptoms over the last two weeks. The total sum of the 8 responses from the PHQ-8 ranges between 0 and 24 with higher scores indicating worse outcome. In general, a total of 10 or above is suggestive of the presence of depression.
- (3) **Change in caregiver self-efficacy.** Self-reported caregiver self-efficacy assessed by the Caregiver Mastery Scale. Total scores can range from 7 to 35, with higher scores reflecting greater caregiver mastery. The Caregiver Mastery Scale is a 7-item measure of self-efficacy. is a 7-item self-report scale, indicating the extent to which respondents agree (5) or disagree (1) with each item. Three items with negative statements are reverse-scored. Total scores can range from 7 to 35, with higher scores reflecting greater caregiver mastery.
- (4) **Change in caregiver stress.** Caregiver stress will be measured on the Kingston Caregiver Stress Scale. This is a 10-item measure with respondents rating the level of stress between 1 (coping fine, no stress) to 5 (extreme stress, feeling at the end of rope). Total scores vary between 10 and 50.
- (5) **Response rates for baseline, 8-week, and 6-month measures.** We will assess participants' willingness to complete study measures using the REDCap online survey by the proportion completing study measures at each time point.
- (6) **Training Completion rate.** We will report training completion rates as a measure of feasibility. Completion will be defined as viewing all 6 online training modules, conducting at least 3 phone calls with a study coach and sending at least one secure message to a study coach in the baseline to 8-week period and one message in weeks 9 through 24.
- (7) **Primary care visit rates.** Measured as the number of primary care visits per eligible study participant during the study period.

- (8) **Urgent care visit rates.** Measured as the number of urgent care visits per eligible study participant during the study period.

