6.4.1 Intervention Arm only

Participants randomized to the intervention arm will also be oriented to the online learning modules. A study coach will give caregivers an overview of the program and assist the caregiver to:

- Navigate to the Kaiser Permanente School learning modules site
- Login using their credentials
- Give an overview of the learning modules, the cadence of completion (one per week), and required homework
- Schedule the first 30-minute check-in regarding Session One of the program.

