6.5 Online Learning Modules

There are 6 self-directed learning modules for intervention arm participants to complete. Modules consist of text, figures and audio describing the principles of the STAR Caregivers program. The modules are:

- (1) Introduction to STAR-Caregivers, Overview of Dementia, Principles of Communication
- (2) ABCs of Problem Solving
- (3) Review of ABCs and Modifying Plans
- (4) Pleasant Events
- (5) Review of Pleasant Events, ABCs, Practical Communication
- (6) Pleasant Events for Caregivers

Each module takes between 30 and 45 minutes to complete and participants are expected to complete one module per week. Participants complete the homework and reading assignments following completion of each module. Study coaches review problem solving plans, pleasant events schedules and any questions about the material or individual needs during follow-up phone calls.

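### Section 7.2.3 puts study arm in the logistic model for training completion, but completion is possible only in the STAR-VTF arm, so the arm coefficient has no finite estimate (minor)

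*Protocol*

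**What the plan says.** Training completion is secondary outcome (6) in Protocol section 3.2 and one of the feasibility measures in Aim 1 (section 2.2). The definition begins: "Completion will be defined as viewing all 6 online training modules, conducting at least 3 phone calls with a study coach". It also requires a caregiver message to a coach in the first 8 weeks and another in weeks 9 through 24.

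These components belong to one arm. Section 6.5 states: "There are 6 self-directed learning modules for intervention arm participants to complete". Section 6.4.1, headed as applying to the intervention arm only, adds: "Participants randomized to the intervention arm will also be oriented to the online learning modules". The Précis describes the comparator as "an attention control group that receives printed materials and links to online training resources but does not receive coaching". Sections 5.3.2 and 5.5 limit control contact to consent, orientation to printed and outside online materials, and 3 scripted outgoing messages.

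For the analysis, section 7.2.3 says: "We will use descriptive statistics to characterize completion rates by study arm and demographic characteristics". It then plans a GEE "to estimate a logistic regression model for completion vs. non-completion", with a covariate list that ends "and caregiver highest level of education attained, and study arm". Section 7.2.1 applies intention to treat to all analyses. Nothing restricts the 7.2.3 model to one arm or names a penalised or exact method. The SAP does not list training completion.

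**The concern.** A binary outcome that cannot occur at one level of a predictor gives quasi-complete separation. The likelihood keeps improving as that predictor's coefficient grows, so ordinary logistic regression, by maximum likelihood or GEE, has no finite estimate for it.

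At stake is one result. If the model is run as written, the output may carry an arm odds ratio with a very small p-value that says nothing about the programme: controls did not complete training that they were not given. If the fit fails visibly instead, the analyst must change a prespecified model after seeing data.

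**Working it through.** **Inputs.** 50 dyads per arm (section 7.1.1). Control completers: 0, from the definition and the description of the arms. STAR-VTF completers k: the documents give no figure, so 20, 30 and 40 of 50 are assumed as a range. Model terms besides arm (section 7.2.3): DSRS, FAQ, PLWD age, PLWD sex, relationship, caregiver age, caregiver sex and caregiver education, which makes 8. The plan gives no numerical figure for completion to reproduce.

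**Step 1: no finite maximum.** With arm alone, the log-likelihood is 50·log(1 − p0) + k·log(p1) + (50 − k)·log(1 − p1). The first term increases until p0 reaches 0, so the log odds ratio, logit(p1) − logit(p0), increases without limit. For k = 25 the limiting value is 50·log(0.5) = −34.657. Newton iterations show the same pattern:

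| Iteration | Log OR | Model-based SE | Log-likelihood |
|---|---|---|---|
| 5 | 6.2 | 1.9 | −34.934 |
| 10 | 11.2 | 23 | −34.659 |
| 15 | 16.2 | 283 | −34.657 |
| 20 | 21.2 | 3,448 | −34.657 |
| 25 | 26.2 | 42,000 | −34.657 |

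The coefficient rises by about 1 per iteration while the likelihood is flat. Its printed value depends on when the program stops.

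**Step 2: what software may print.** statsmodels GEE was fitted with a binomial family, independence working correlation, one record per dyad, arm plus 8 simulated covariates unrelated to completion, and 500 datasets per k. All 1,500 fits were flagged as converged.

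| k of 50 | Median log OR | Median robust SE (5th–95th percentile) | z (ratio of medians) |
|---|---|---|---|
| 20 | 25.5 | 0.53 (0.36–1.04) | 48 |
| 30 | 26.4 | 0.58 (0.38–1.27) | 45 |
| 40 | 28.0 | 1.04 (0.53–2.78) | 27 |

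The robust error is small for a mechanical reason. With arm alone, the control arm adds 50·p0² / [50·p0(1 − p0)]² to the variance, which tends to 1/50 as p0 tends to 0. The median model-based SE was 46,000 to 47,000. Plain logistic regression in the same package, at default settings, failed visibly in 277, 286 and 289 of 300 datasets at k = 20, 30 and 40.

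**Step 3: the other coefficients.** The largest difference between the covariate coefficients of the two-arm fit with arm and those of a STAR-VTF-only fit had a median of about 5e-13 or less. Rare exceptions at k = 40 reached 0.96. Control dyads therefore add essentially nothing to these coefficients. If the arm term is removed but the control dyads stay in, all 50 enter as non-completers and the covariate coefficients move: the median of the largest shift was roughly 0.4 to 1.1 log-odds across simulations.

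**Step 4: what can be reported.** Exact (Clopper-Pearson) 95% intervals for the STAR-VTF rate are 26% to 55% at 20/50, 45% to 74% at 30/50 and 66% to 90% at 40/50. For a within-arm model the limiting count is the smaller of completers and non-completers, at most 25. That gives 25/8 = 3.1 events per term at best, 20/8 = 2.5 at 20/50 or 30/50, and 10/8 = 1.25 at 40/50. The median SE for an evenly split binary covariate was 0.70 at 30/50, so its 95% interval is the odds ratio multiplied or divided by exp(1.96 × 0.70) = 3.9. At 40/50 the SE was 0.89 and the factor 5.8 (unrounded SE).

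**The case against.** The strongest reply is that no arm comparison of completion is promised. Aim 1 and outcome (6) ask for a rate, and the stated hypotheses, H1 and H2 in Aim 3, concern burden and antipsychotic use. Arm stands last in an adjustment list that nearly repeats those in sections 7.2.2, 7.2.5 and 7.2.6, where it makes sense, so it may simply have been carried over. This stands as to weight and is the main reason the point is minor. The model as written still contains a term that it cannot estimate.

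Four stronger readings might be inferred, and the documents and checks do not support them:

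- **The planned software will silently report a huge arm effect.** This was seen in statsmodels GEE only. The SAP names Stata 17.0, which was not tested.
- **The p-value is equally likely to be near 0 or near 1.** Section 7.2.3 names no standard error, but 7.2.5 and the burden model in 7.2.6 specify robust errors. The model-based version is the less natural reading.
- **Describing completion by arm is also an error.** A control row of 0% in a table is uninformative but harmless.
- **Deleting the arm term is enough.** Step 3 shows that this alone would distort the other coefficients.

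A penalised fit would give a finite arm coefficient, but the plan names none, and the contrast would still only restate the design.

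**Conclusion.** The point holds and is minor. Control completion is zero by design, so the arm coefficient in the 7.2.3 model has no finite estimate. This follows from the protocol's own definitions and does not depend on the assumed number of STAR-VTF completers. The printed values do depend on that assumption, on simulated covariates and on the software.

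A reader might infer that the feasibility result or the trial's main conclusions are compromised. They are not. The STAR-VTF completion rate and the primary burden outcome are untouched, and the remaining coefficients are, with rare exceptions, those of a STAR-VTF-only fit.

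**What to change.** In section 7.2.3, restrict the completion model to the STAR-VTF arm and, as part of the same change, remove the study arm term. Keep the completion definition in 3.2. The descriptive table may stay by arm or be limited to STAR-VTF.

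Suggested wording: *The training completion rate in the STAR-VTF arm will be reported with an exact (Clopper-Pearson) 95% confidence interval and described by demographic characteristics. A logistic model for completion will be fitted in the STAR-VTF arm only, using the listed PLWD and caregiver covariates. This model is exploratory.*

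The exploratory label is needed because at most 25 events for 8 terms gives imprecise estimates; a shorter covariate list would help. The cost is wording only, with no new data. Once the model is confined to STAR-VTF, dropping the arm term loses no information.

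### The visit-rate Poisson GEEs in Protocol 7.2.5 name no small-sample correction; with a plain sandwich and z reference, a nominal 5% test rejects about 7% to 9% of the time

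*Protocol*

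**What the plan says.** **Visit rates (Protocol 7.2.5).** The plan is: "We will use longitudinal, generalized estimating equations (GEE) to estimate a Poisson regression model for adjusted mean monthly visit rates", separately by visit type, over six months. On precision it says "We will use the robust sandwich estimator to calculate standard errors", because each person contributes six monthly observations and the Poisson variance may be wrong. The adjustment set is DSRS, FAQ, age and sex of the person with dementia, caregiver relationship, caregiver age and sex, and caregiver education, plus arm.

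**Burden (Protocol 7.2.6).** A GEE with the same eight covariates, "using robust sandwich estimators to calculate standard errors accounting for within person correlation". Section 7.2.7 uses GEE again for the PHQ-8, mastery and Kingston scales and does not say how standard errors are formed.

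**Size and error rate (Protocol 7.1 and 7.1.1).** "We anticipate enrolling 100 PLWD-CG dyads in the trial (50 per arm), with up to 90 remaining enrolled at 6 months of follow-up". The type I error appears only in the power calculation for the RMBPC: "Assuming an effect size of 0.65, type-I error of 0.05, power of 80%, and equal sample sizes".

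**SAP.** The RMBPC, mastery and Kingston scales are analysed by ordinary least squares with empirical standard errors, adjusted for gender, age and baseline score. The SAP does not mention visit rates or the PHQ-8.

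Neither document names a small-sample correction for the sandwich or a reference distribution.

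**The concern.** The sandwich is a sensible choice for overdispersed repeated counts. Its plain form, however, is built from fitted residuals, which are smaller than the true errors by an amount that grows with the number of parameters per independent cluster. The dyad is the cluster here, so six monthly records per person do not help. With about 10 to 12 parameters and 90 to 100 dyads the shortfall is not negligible, and skewed counts add to it.

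At stake are the confidence intervals for three visit-rate ratios. These belong to the payer-perspective aim, and 7.2.5 is their only specification. To a lesser degree the burden effect is also affected, if the Protocol's GEE is the model used.

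**Working it through.** **1. Reproduce the plan's own figure.** n per arm = 2(z₀.₉₇₅ + z₀.₈₀)²/d² = 2(1.960 + 0.842)²/0.65² = 37.2, so 38 by the normal formula. With the noncentral t, power is 0.7985 at 38 and 0.809 at 39. The Protocol's 39 per arm is therefore right for a two-sided 5% test. 39 × 1.3 = 50.7, stated as 50 per arm; 100 × 0.9 = 90 at 6 months.

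**2. Count parameters.** Eight covariates plus arm make 9 terms, or 10 parameters with the intercept. If education has four categories (an assumption; the coding is not given) there are 11 terms and 12 parameters.

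**3. Rough analytic size.** Average leverage is p/n, between 10/100 = 0.10 and 12/90 = 0.133. The plain sandwich variance is too small by roughly that fraction.
- SE ratio √0.90 = 0.949: effective cut-off 1.96 × 0.949 = 1.86, two-sided rejection about 6.3%.
- SE ratio √0.867 = 0.931: effective cut-off 1.825, rejection about 6.8%.

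This covers leverage only. Variability of the variance estimate and skewness push the rate higher.

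**4. Simulation of the Poisson visit model under the null.** The documents give no visit rates or overdispersion. Assumed: means of 0.5, 1, 3 and 6 visits per 6 months, with gamma frailty of shape 0.7 to 5. Covariates are constant within dyad and follow-up is equal, so an independence GEE on monthly counts is the same as a fit to dyad totals. About 6,000 runs per setting; Monte Carlo SE about 0.35 points. Rejection (%) at nominal 5%, range over the four visit-rate settings:

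| Dyads | Terms | Plain, z | n/(n-p), t | Kauermann-Carroll, t | Mancl-DeRouen, t |
|---|---|---|---|---|---|
| 90 | 9 | 7.5–8.1 | 5.7–6.1 | 5.5–5.7 | 3.6–4.1 |
| 90 | 11 | 7.7–9.1 | 5.6–6.4 | 5.3–5.7 | 3.2–3.7 |
| 100 | 9 | 6.9–8.3 | 5.4–6.3 | 5.2–5.9 | 3.7–4.6 |
| 100 | 11 | 7.7–8.5 | 5.6–6.2 | 5.2–5.8 | 3.5–3.8 |

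Repeat simulations, with means down to 0.4 visits, widen the ranges to 6.7–9.4 (plain, z), 5.1–6.7 (n/(n-p), t), 4.6–6.6 (Kauermann-Carroll, t) and 3.0–4.7 (Mancl-DeRouen, t). An n/(n-1) factor alone removes only 0.1 to 0.2 points. A direct exchangeable GEE on six monthly counts at 100 dyads gave 7.9% (1,000 runs, Monte Carlo SE 0.85 points).

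**5. What 7% to 9% means for intervals.** Coverage of a 95% interval is about 91% to 93%. Treating the statistic as normal, the reported SE is 1.812/1.960 = 0.92 down to 1.695/1.960 = 0.865 of what is needed, so intervals are about 8% to 13% too narrow.

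**6. Other models.**
- Burden GEE (Gaussian, plain with z): 6.7% to 6.9% at 100 dyads and 7.1% to 7.2% at 90. Variants, including one with time terms and within-person correlation 0.6, span about 6.5% to 7.8%. With n/(n-p) or Kauermann-Carroll and t: 4.9% to 5.4%.
- Logistic refill GEE (assumed 60% event rate, 11 terms): 5.8% at 90 and 6.3% at 100.
- SAP least squares model (about 4 terms): 5.9% to 6.1% plain with z; 4.9% to 5.1% with n/(n-p) and t.

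**The case against.** A reader might infer that the trial as a whole runs at 7% to 9% against a promised 5%. The documents do not support that.

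- That the sandwich is uncorrected and referred to z is inferred from silence. The Protocol names no correction but rules none out.
- The 0.05 is stated only for the RMBPC power calculation. Section 7.2.5 states no alpha, and visit rates are secondary outcomes.
- The upper range belongs to the Poisson models. The burden excess is nearer 2 points and the refill excess about 1.
- Eleven terms requires education in four categories; the listed terms number 9.
- For the RMBPC, mastery and Kingston scales the SAP has a shorter model, which holds about 5% if its robust variance uses n/(n-p) and t.

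All of this stands, and it limits the point. It does not remove it. With 9 terms the visit-rate result is still 6.9% to 8.3%. The plain sandwich with z is an ordinary reading of the text. The SAP offers no alternative for visit rates or the PHQ-8, and it does not state the scaling or reference distribution on which its own 5% depends.

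**Conclusion.** The point holds for the visit-rate GEEs in 7.2.5. Applied in its plain form with a z reference, the stated method would reject a true null about 7% to 9% of the time at nominal 5%, which is 40% to 80% more false positives (2/5 to 4/5). This is a conditional result. It rests on no correction being applied, assumed means of 0.4 to 6 visits per 6 months, assumed gamma overdispersion, equal follow-up, and 9 to 11 model terms.

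For the burden GEE in 7.2.6 the figure is about 6.5% to 7.8% at 90 to 100 dyads, against the 0.05 used for power. It applies only if the Protocol's model, not the SAP's, is the one reported. The sample-size calculation itself is sound.

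**What to change.** In 7.2.5, and in 7.2.6 and 7.2.7 wherever GEE is kept, state that standard errors come from a Kauermann-Carroll corrected sandwich clustered on dyad (or at least one scaled by n/(n-p)), and that tests and intervals use a t distribution on dyads minus parameters. The resulting rate is about 5% to 7% for visit rates and about 5% for burden. Do not list Mancl-DeRouen as interchangeable, because with t it over-corrects to about 3% to 5%.

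For the scale outcomes, say whether the Protocol's GEE or the SAP's least squares model is the analysis. If it is the latter, state n/(n-p) robust standard errors with a t reference. The SAP should also cover visit rates and the PHQ-8, or point to the Protocol for them.

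The covariate list need not change for this purpose; shortening it is a separate trade-off.

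**Cost.** A few lines of text and wider intervals. With n/(n-p) and t, the widening runs from √(100/90) × 1.987/1.960 = 1.07 (100 dyads, 10 parameters) to √(90/78) × 1.991/1.960 = 1.09 (90 dyads, 12 parameters), or about 7% to 9%.
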